6.3.5 Study Medication Weaning

After VentaProst dose stabilization, patients will be weaned from VentaProst. VentaProst weaning will occur from mechanical ventilation only. If the patient has been extubated and is on institution's standard of care delivery for administering aerosolized Veletri, weaning will occur in accordance with each site's standard of care guideline for weaning of aerosolized Veletri.

Patients on mechanical ventilation will be weaned from VentaProst slowly due to concern that VentaProst is providing significant clinical benefit and to avoid a rebound effect. Doses will be decreased in increments of 20% of the VentaProst equivalent dose, with a minimum of 30 minutes between changes, down to 20% of the dose before discontinuation. The VentaProst weaning process should occur in isolation to other treatment changes (no changes in inotropes, vasopressors or vasodilators). Patients will be observed closely before, during, and after dosing changes. In the event patients demonstrate signs of hemodynamic instability (changes in combined hemodynamic parameters) or a decrease in oxygenation indicated by either arterial or central blood oxygenation saturation during downward titration, the VentaProst dose will be returned to its previous level. Once patients have been stable for at least 15 minutes, repeat attempts at dose reduction may be undertaken. The process will continue until patients are fully weaned from VentaProst.

6.4 Identity of the Device Component of the Investigational Product

6.4.1 Identity of Device

The Phase 2a VentaProst drug delivery system is designed to accurately and precisely administer aerosol to the lungs of critically ill patients who require support via mechanical ventilation. The aerosol generator's fundamental operating mechanism and

materials of construction will be similar to the 510(k)-cleared Aeroneb Solo System (K120939, K103635, K070642, Aerogen Ltd) and it is being designed for compatibility with the range of ventilators found in the OR and ICU.

6.4.1.1 Aerosol Delivery to Ventilated Patients

The Phase 2a VentaProst drug delivery system (Figure 1) consists of reusable and single-patient disposable elements:

- Reusable multi-patient use components consist of two electronic controllers, Aerogen Solo Nebulizer Cable, and Sensirion Flow Sensor Cable. When used together, they synchronize aerosol generation with the patient's inspiratory pattern through a single-patient use, disposable administration kit.
 - Aerogen Pro-X, a device to continuously operate the disposable Aerogen Solo nebulizer.
 - Aerogen Pharma Controller, which synchronizes aerosol generation with the ventilator breathing pattern.
 - Aerogen Solo Nebulizer Cable
 - Sensirion Flow Sensor Cable
- Single-patient disposable kit:
 - Aerogen Solo Nebulizer - a low mass and low profile vibrating mesh aerosol generator.
 - Aerogen Continuous Nebulization Tube Set (CNTS) and syringe connected to the nebulizer.
 - Sensirion Flow Sensor.

[figure not shown]

Figure 1 – Drug Delivery System

Prior to VentaProst administration, the study medication will be reconstituted in the recommended diluent buffer and placed into the CNTS syringe. The user will attach the syringe to the CNTS tubing and prime the tube set so that the formulation reaches the Aerogen Solo, producing aerosol generation. The CNTS syringe set will be placed in a B Braun Perfusor Space Infusion syringe pump. The 15-mm T-Piece with nebulizer is placed between the ventilator circuit and the ETT (Figure 2). The user will select the pump rate to deliver the recommended dose based on the ideal body weight in kilograms (kg) dispensed to achieve the dose rate in ng/kg/min. The user will be able to adjust this recommended dose up or down (per protocol) by changing pump rate prior to selecting dose and initiating delivery. The selected dose will then be dispensed by the pump to the receiving surface of the mesh, resulting in generation of an aerosol with a volume median diameter in the range of 2 to 5 μm . The Aerogen Pharma Controller monitors the patient's breathing pattern and user adjusts the knob (on left) to initiate aerosol generation at the beginning of the breathing cycle. The knob on right sets the duration of aerosol generation within each breath.

[figure not shown]

Figure 2 - VentaProst Device Placement in the Gas Pathway

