Study Design	
Part I (see Appendix 1 for Study Design Schematic)
 
The first part of this study will be conducted in approximately 10 consented post-operative cardiothoracic surgery patients on cardiopulmonary bypass (CPB) who are receiving aerosolized Veletri (in accordance with each site's standard of care guidelines) and who demonstrate at least a 15% improvement in one or more hemodynamic parameters (as defined by the clinical team) when treated with aerosolized Veletri. This part of the study is designed to demonstrate the dose equivalence between aerosolized Veletri and VentaProst using a patient's hemodynamic parameters, with the goal to determine the VentaProst dose necessary to achieve a hemodynamic response that is not less than 90% of the effect observed with 50 ng/kg/min aerosolized Veletri. Arterial oxygen saturation (SaO₂) must be maintained at or above the level obtained with aerosolized Veletri administration.
 
Qualifying patients will:
 
 • Receive aerosolized Veletri 50 ng/kg/min in the OR/ICU • Have hemodynamic parameters measured before and after aerosolized Veletri administration to determine changes 
 ○ IF AT LEAST A 15% IMPROVEMENT IN ONE OR MORE HEMODYNAMIC PARAMETERS (AS DEFINED BY THE CLINICAL TEAM) IS SEEN WITH AEROSOLIZED VELETRI AFTER STABILIZATION IN THE ICU:

- Be administered VentaProst as follows: Setup VentaProst inline to the ventilator circuit, start nebulization, then stop conventional Veletri pump flow and nebulizer while still inline. Do not remove Veletri administration system until VentaProst administration is confirmed
- *IF LESS THAN A 15% IMPROVEMENT IN ONE OR MORE HEMODYNAMIC PARAMETERS (AS DEFINED BY THE CLINICAL TEAM) IS SEEN WITH AEROSOLIZED VELETRI AFTER STABILIZATION IN THE ICU:*
 - Not be administered VentaProst
- Receive a calculated equivalent starting dose of 17 ng/kg/min of VentaProst while still on mechanical ventilation
- Receive increases in the VentaProst dose in 20% increments (refer to the VentaProst Pharmacy Manual) every 15 minutes until at least 90% of the hemodynamic effect observed with 50 ng/kg/min aerosolized Veletri is achieved while still on mechanical ventilation

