	
b. Hemoglobin < 9 gm/dL, white blood count (WBC) count < 2500 mm³, neutrophil count < 1500 mm³, platelet count < 100 × 10³/ mm³
 
c. Evidence of hemoglobinopathy (including but not limited to sickle cell disease, thalassemia, hemoglobin M and variants with high oxygen affinity).
 
13. Pregnant or breastfeeding
 
14. Treatment with an investigational drug, biologic, or investigational cardiac implant within 30 days preceding the first dose of study medication or plans to take another investigational drug or biologic within 30 days of study completion
 
15. Other severe, acute, or chronic medical or psychiatric condition or laboratory abnormality that may increase the risk associated with trial participation or investigational product administration or may interfere with the interpretation of trial results and, in the judgment of the Investigator or Sponsor, would make the patient inappropriate for entry into this trial
 
16. Any condition where aerosolized epoprostenol is contraindicated
 
17. Known allergy or sensitivity to epoprostenol, any of its ingredients, or the diluent (glycine)

Study Treatment(s)	
Part I
 
Study treatments are:
 
 • Aerosolized Veletri 50 ng/kg/min administered in accordance with each site's standard of care guidelines • VentaProst Patients who demonstrate at least a 15% improvement in one or more hemodynamic parameters (as defined by the clinical team) with aerosolized Veletri will be crossed over to a calculated VentaProst equivalent dose of 17 ng/kg/min with subsequent dose titration increases of 20% increments (refer to VentaProst Pharmacy Manual) every 15 minutes until a hemodynamic response that is not less than 90% of the effect observed with 50 ng/kg/min aerosolized Veletri is achieved. 
Part II
 
Study treatment is VentaProst at a starting dose of 3.4 ng/kg/min of VentaProst, followed by 3.4 ng/kg/min dose titration increases (refer to VentaProst Pharmacy Manual) every 5 to 15 minutes as clinically indicated until no further improvements in one or more hemodynamic parameters are achieved. VentaProst doses will be decreased to the prior level once a dose response plateau is observed.

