Epoprostenol is metabolized to 6-keto-PGF1 α (formed by spontaneous degradation) and 6,15-diketo-13,14-dihydro-PGF1 α (enzymatically formed), both of which have pharmacological activity at orders of magnitude less than epoprostenol in animal test systems. 6-keto-PGF1 α has been used as a surrogate PK metabolite for epoprostenol, but does not accurately represent the local active concentration of epoprostenol in the lungs with an elimination half-life of approximately 20-30 minutes. Additionally, large and rapid fluctuations in endogenous epoprostenol as indicated by 6-keto-PGF1 α levels perioperatively in cardiac surgery confound the exogenous epoprostenol contribution for PK determinations (Ylikorkala 1981).

Inhalation delivery of epoprostenol in cardiothoracic surgery patients offers an attractive alternative to IV delivery because it minimizes systemic exposure associated with clinically hazardous effects such as hypotension and exacerbation of pulmonary and cardiac shunts. The rationale for administering epoprostenol continuously as an aerosol through ventilator support equipment stems from its extremely short half-life of approximately three minutes *in vivo*. This enables delivery of high local concentrations of vasodilator into the lung vasculature, reducing PVR (pulmonary vascular resistance)

and RH (right heart) afterload. As a result, the use and effectiveness of inhaled epoprostenol is widely reported [Buckley and Feldman, 2010; De Wet, 2004; Fattouch, 2005; Fattouch, 2006; Hache, 2003; Haraldsson, 2001; Khan, 2009; Ocal, 2005] in a variety of applications including mitral valve surgery. Nonetheless, such practices remain off-label, as inhaled epoprostenol is not FDA-approved for this indication or route of administration.

Clinical centers have independently developed protocols to deliver the IV formulation as aerosol by mechanical ventilation and nasal cannula using commercially available nebulizers. The nominally prescribed dose of 50 ng/kg/min is administered without regard for system efficiencies with these protocols. This results in dose delivery to the lungs that is assumed to be within the flat portion of the hemodynamic dose response curve to inhaled epoprostenol.

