A review of published literature demonstrates that the use of inhaled epoprostenol in patients undergoing cardiothoracic surgery is safe and well tolerated. Doses of 10 – 100 ng/kg/min administered through a wide variety of conventional aerosol delivery methods led to improved hemodynamics (such as lowering of pulmonary arterial pressure [PAP] and pulmonary vascular resistance [PVR]), improved cardiac index (CI) and right ventricular ejection fraction (RVEF), easier separation from CPB, reduced intubation times, and shorter stays in the ICU.

The VentaProst nebulizer delivery platform is designed to accurately and precisely administer aerosol to the lungs of critically ill patients requiring support via mechanical ventilation and/or supplemental oxygen by nasal cannula. The intent is to standardize the critical components for consistent and quantifiable aerosolized epoprostenol delivery by mechanical ventilator and nasal cannula systems. Aerogen Pharma has evaluated various delivery systems used for conventional aerosol administration of epoprostenol to the lungs (in accordance with each site's standard of care practice guideline) and has estimated the equivalent dose by VentaProst.

The intent of Part I of the Phase 2a study is to demonstrate that the estimated VentaProst dose has the same hemodynamic effect as aerosolized Veletri at 50 ng/kg/min (in accordance with each site's standard of care guidelines). The assumption is that the hemodynamic response from the aerosolized Veletri dose will not change significantly with minor changes in dose (flat portion of the dose response curve). When patients are converted to VentaProst, a determination is made whether or not the hemodynamic response is similar by being at least as much as the response with the aerosolized epoprostenol dose. If the hemodynamic response with VentaProst is less than that of the aerosolized Veletri dose, the dose will be increased until a similar response is observed. VentaProst dosing will not be titrated downward to match the aerosolized Veletri hemodynamic response because of the possibility that the patients' requirements for pulmonary vasodilation may have improved since the start of aerosolized Veletri.

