3. STUDY OBJECTIVES

3.1 Primary Objective

The primary objective of this study is to identify the relative dose equivalency between effective conventionally administered aerosolized Veletri and VentaProst doses.

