6.3.3 Study Medication Administration

6.3.3.1 Part I

Aerosolized Veletri 50 ng/kg/min will be administered to study patients in the OR or the ICU in accordance with each site's standard of care guidelines on administration of aerosolized Veletri. In the ICU, patients who demonstrate a clinically meaningful hemodynamic response (i.e., at least a 15% improvement in one or more hemodynamic parameters) to aerosolized Veletri will be crossed over to a calculated VentaProst equivalent dose of 17 ng/kg/min to be administered through a custom nebulizer delivery system. The VentaProst dose will then be increased in 20% increments (refer to VentaProst Pharmacy Manual) every 15 minutes to match the clinically meaningful PD measures achieved (i.e., not less than 90% of the effect observed) with the aerosolized Veletri dose.

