10.1.3 Aerosolized Veletri Treatment (OR/ICU)

If there is a need for administration of aerosolized Veletri, the patient will begin dosing at 50 ng/kg/min (in accordance with each site's standard of care guidelines) and will undergo the following study-related procedures and evaluations:

- Measure hemodynamic, oxygenation, and ventilator parameters before aerosolized Veletri administration and after stabilization of aerosolized Veletri
- If at least a 15% improvement in one or more hemodynamic parameters (as defined by the clinical team) is seen with aerosolized Veletri after stabilization in the ICU, the VentaProst will be set-up inline to the ventilator circuit, VentaProst nebulization will be started, and then the Veletri pump flow will be stopped once VentaProst administration is confirmed. Do not remove Veletri administration system until VentaProst administration is confirmed
- If less than a 15% improvement is seen in one or more hemodynamic parameters (as defined by the clinical team) with aerosolized Veletri after stabilization in the ICU, the patient will not be administered VentaProst
- Record all concomitant medications
- Investigator assessment of any unanticipated medical events

If the patient does not require aerosolized Veletri, or if the patient fails to achieve at least a 15% improvement in one or more hemodynamic parameters with aerosolized Veletri, the patient will be withdrawn from the study as a screen failure.

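### VentaProst is dosed per kg of ideal body weight, but the weight behind Veletri's nominal 50 ng/kg/min is neither stated nor recorded, so the equivalence figure may mix two weight bases

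*Combined protocol and SAP*

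**What the plan says.** The primary objective (3.1) is to "identify the relative dose equivalency between effective conventionally administered aerosolized Veletri and VentaProst doses". The endpoint (7.1, 12.5.1) is the VentaProst dose that gives at least 90% of the effect of Veletri at 50 ng/kg/min. Both products are expressed in ng/kg/min.

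For VentaProst the kilogram is defined. Section 6.4.1.1 sets the pump rate to "deliver the recommended dose based on the ideal body weight in kilograms (kg".

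For Veletri it is not. The Synopsis lists "Aerosolized Veletri 50 ng/kg/min administered in accordance with each site's standard of care guidelines", section 6.3.3.1 repeats this for both settings, and 10.1.3 says "the patient will begin dosing at 50 ng/kg/min (in accordance with each site's standard of care guidelines". The nominal rate is therefore fixed. The weight it multiplies and the delivery method are left to about three sites, and the Introduction (2.1) says that clinical centres developed their delivery protocols independently.

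Measured weight and height are taken at Screening (8.1.1, 10.1.1). The dispensing log in 6.3.1 holds patient number, dose number, date and time. No section asks for the weight used to dose Veletri, its basis, or the ng/min rate of either product, and 12.5.1 is silent on weight.

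**The concern.** A conversion between two per-kg doses can be read as a relative dose only if both use the same kilogram. If a site computes Veletri on actual weight, the statement that 50 ng/kg/min of Veletri equals X ng/kg/min of VentaProst sets mass per actual kg against mass per ideal kg. The hemodynamic match within each patient is unaffected. The number taken from that match would also carry the patient's ratio of Veletri dosing weight to ideal weight.

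That component would come on top of the differences in delivery efficiency that the study sets out to quantify. The Introduction already says of conventional practice that "The nominally prescribed dose of 50 ng/kg/min is administered without regard for system efficiencies with these protocols". With about 10 patients in Part I and descriptive summaries only, a basis difference between sites would look like a difference between delivery systems or patients. The resulting conversion would not carry over to a centre that uses another weight.

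**Working it through.** **The plan's own figure.** The starting point is "Receive a calculated equivalent starting dose of 17 ng/kg/min of VentaProst while still on mechanical ventilation" (Synopsis). It implies 17/50 = 0.34, or 50/17 = 2.94. The source is given only as an evaluation from which the sponsor "has estimated the equivalent dose by VentaProst" (2.1). No efficiencies or weights are shown, so 17 cannot be re-derived. The one available check holds: 20% of 17 is 3.4, the Part II step.

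**Assumption.** Let r = Veletri dosing weight / ideal weight. The documents give no value, so r = 1.0, 1.2, 1.4 and 1.6 are used for illustration.

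**Case (a): relative efficiency constant at 17/50.** A Veletri rate of 50 per dosing kg is 50r per ideal kg. The mass-matched VentaProst dose is 50r × 0.34 = 17r, and the nominal ratio is 50/(17r).

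**Case (b): response flat, every patient matches at 17.** The reported ratio is 50/17 throughout. The ratio of pumped ng/min (Veletri to VentaProst) is 50r/17. For an ideal weight of 70 kg, VentaProst runs at 17 × 70 = 1190 ng/min, and Veletri at 50 × 70 × r = 3500, 4200, 4900 or 5600 ng/min.

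| r | (a) matched dose, ng/kg ideal/min | (a) nominal ratio | (b) reported ratio | (b) mass ratio |
|---|---|---|---|---|
| 1.0 | 17.0 | 2.94 | 2.94 | 2.94 |
| 1.2 | 20.4 | 2.45 | 2.94 | 3.53 |
| 1.4 | 23.8 | 2.10 | 2.94 | 4.12 |
| 1.6 | 27.2 | 1.84 | 2.94 | 4.71 |

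In case (a), r = 1.2 is worth one full 20% titration step. If five patients come from a site with r = 1.4 and five from a site with r = 1.0, the mean matched dose is (5 × 23.8 + 5 × 17.0)/10 = 20.4. The SD is 3.4 × √(10/9) = 3.58 and the CV 17.6%, from weight basis alone.

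For r below 1 the matched dose would be 13.6 (r = 0.8) or 15.3 (r = 0.9). Section 2.1 rules out downward titration to match, so both would be recorded as 17.

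**Which case is nearer depends on the dose-response curve.** Assume an Emax curve with ED50 in Veletri ng/kg ideal/min and relative efficiency 0.34. The VentaProst dose needed for 90% of the Veletri effect is:

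- ED50 10: 13.6 at r = 1.6, so 17 suffices.
- ED50 25: 16.7 at r = 1.4 and 18.6 at r = 1.6, so 17 fails only at the latter.
- ED50 50: 18.8 at r = 1.4 and 21.1 at r = 1.6, so 17 fails at both.

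On a flat curve the study behaves like (b); on a steeper one it moves towards (a).

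**The case against.** The strongest reply is that the documents show silence, not conflict. Nothing says that any site doses Veletri on actual weight. The site guidelines, the Pharmacy Manual, the eCRF guidelines and the detailed analysis plan promised in 12.1 are not available here, and one of them may settle the basis or capture pump rates. This stands: the mismatch is conditional, and the values of r are assumed.

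Second, the endpoint is worded as a VentaProst dose matched to nominal Veletri practice, not as a ratio. A pragmatic conversion of that kind is legitimate. This also stands, and it is why the stated endpoint should be kept. But the objective speaks of relative dose equivalency, and the endpoint alone does not deliver that if the kilograms differ.

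Third, a reader might infer that the weight effect could never be separated. That is too strong. Height and weight are collected, medications are recorded (6.6), hospital charts are source documents (13.2.3), and a site's basis could be asked for. The accurate statement is that separation is not planned and the key items are not required.

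Fourth, if response is flat, 17 may match whatever the basis. This is possible, but 2.1 presents flatness as an assumption about minor dose changes, and r = 1.4 is a 40% difference. If it does hold, the mismatch is hidden rather than removed.

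**Conclusion.** The point holds in conditional form. The plan defines the weight for one product and not the other, and requires nothing that would show whether they agree. The error is zero if every site doses Veletri on ideal weight. Otherwise, for r up to an assumed 1.6, either the matched dose rises to as much as 27.2 and the nominal ratio falls to 1.84 (constant efficiency), or the reported 2.94 conceals a mass ratio of up to 4.71 (flat response).

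Three stronger readings are not supported. A reader might infer that the reported ratio must move with body size, but in case (b) it does not move at all. A reader might infer that the figure would reflect weight instead of delivery efficiency, but the weight component is added to efficiency and confounded with it. A reader might infer that the Veletri rate itself is left to the sites, but it is nominally fixed at 50 ng/kg/min.

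This is not a claim about patient safety or about which weight should be used for dosing. It should be fixed because it bears on the trial's main number and the missing items are hard to recover afterwards.

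**What to change.** Leave dosing unchanged.

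- **10.1.3 and 10.1.4.1:** record in the eCRF, for each product, the dosing weight, its basis, and the rate delivered in ng/min (pump rate × concentration). Take the rate at the Veletri reference reading and again at the VentaProst match.
- **12.5.1 and the SAP:** keep the stated endpoint, the VentaProst ng/kg/min that matches nominal Veletri 50. Add the per-patient ratio of the two ng/min rates as the measure of relative dose equivalency; it does not depend on any weight. Also show both doses recomputed on one common weight, listed by site. Screening height and weight allow this once the formula for ideal weight is stated.

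With both products in ng/min, or on one weight, r drops out. At constant efficiency the ratio is then 2.94 for every body size and site, and any remaining spread reflects delivery and response.

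The cost is a few eCRF fields taken from pump records and one added definition. The headline ratio may then differ from the nominal 50:17.
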